### 3. Abstract:

Loss of mobility and cognitive ability are serious conditions that threaten the independence of older adults. Importantly, both of these conditions are mechanistically linked by impairment of frontal lobe brain function. Frontal lobe dysfunction has been implicated as a factor contributing to gait deficits in some individuals with Alzheimer's disease, frontotemporal dementia and vascular dementia. There is a critical gap in knowledge about what therapeutic strategies are effective for maintaining or reinstating function in this critical brain region in order to preserve physical and cognitive health in older adults. The goal of our research is to develop a novel therapeutic intervention to enhance both mobility and cognition via neuroplasticity of frontal/executive control circuits. We will engage neuroplasticity of frontal circuits in two ways. The first is through neurorehabilitation with "complex walking tasks" (CWTs), such as obstacle crossing, obstacle avoidance and walking on non-uniform surfaces. CWTs are a potent behavioral approach for engaging prefrontal circuits. Furthermore, CWTs are crucial to successful ambulation in the home and community settings and therefore provide an ecologically valid therapeutic approach. The second approach that we will use to engage neuroplasticity of frontal circuits is anodal transcranial direct current stimulation (tDCS). Anodal tDCS is a safe, non-invasive neuromodulation technique. It has previously been shown to induce excitatory effects on brain tissue and, in single-session assessments, to improve performance during complex walking tasks. tDCS has also been shown to be an effective adjuvant for enhancing the effects of cognitive training. The objective of this study is to calculate effect size, establish variance of response and demonstrate feasibility of the experimental interventions in order to plan for a full scale clinical trial. Participants will include thirty older adults who demonstrate evidence of frontal/executive impairment. Participants will be randomized to one of three groups: 1) standard walking neurorehabilitation with sham tDCS ('standard/sham' group), 2) complex walking neurorehabilitation with sham tDCS ('complex/sham' group), or 3) complex walking neurorehabilitation with active anodal tDCS ('complex/active' group). Functional near infrared spectroscopy (fNIRS) will be used to explore intervention-induced changes in prefrontal cortical activity. Assessments will be conducted at baseline, post-treatment and 3-month follow up. We propose the following specific aims:  
Specific Aim 1: Determine preliminary efficacy for recovery of mobility and cognitive function.  
Specific Aim 2: Demonstrate feasibility/safety of tDCS as an adjuvant to rehabilitation.  
Specific Aim 3: Explore the relationship between prefrontal activity and behavioral outcomes  
The data collected here will provide the information needed to justify and plan a future full scale clinical trial to assess the relative efficacy and underlying mechanisms of each intervention approach.

#### **4. Background:**

Age-related mobility deficits and/or cognitive deficits are present in a large proportion of older adults. Those who have mobility deficits have higher rates of morbidity and mortality, more hospitalizations, poorer quality of life, and are less likely to remain independent. Those who have cognitive deficits experience reduced ability to perform instrumental activities of daily living and have a reduced quality of life. Standard therapeutic approaches are insufficient for addressing age-related impairment of physical and cognitive function. There is a clear and urgent need for alternative or adjuvant strategies that can directly target specific mechanisms of impairment in order to yield greater gains. Deficits in cerebral function are known to affect cognition, and are also likely to be an important mechanism contributing to mobility deficits. Physical interventions that are designed to target cerebral mechanisms may not only improve walking function, but may also improve cognitive function. Directly combating age-related dysfunction of frontal/executive circuits may considerably enhance mobility and cognitive function.

The important role of cerebral structure and function on walking and cognitive ability is made clear by the often devastating effects of overt neurological injury/disease such as stroke, traumatic brain injury, Parkinson's disease and Alzheimer's Disease. A less appreciated issue is that older adults also exhibit substantial but sub-clinical impairments of cerebral structure and function. These impairments include (but are not limited to) reduced intracortical excitability, reduced cortical thickness, loss of gray matter volume and increased presence of white matter hyperintensities [42-49]. Accumulating evidence indicates that age-related degradation of the brain is a common and important factor contributing to decline of mobility and cognition.

Frontal cerebral circuits are particularly important because they have broad effects on executive functions that are important to planning, initiating and coordinating both cognitive and motor behaviors. Our recent research suggests that older adults who exhibit a greater level of prefrontal cerebral activity (measured by fNIRS) during complex walking tasks also perform those tasks better. Evidence also indicates that the prefrontal cortex and other frontal lobe brain regions are particularly susceptible to age-related dysfunction. The prefrontal cortex is an important component of multiple major cerebral circuits that have been linked to walking function.

#### Neurorehabilitation of Walking

Neurorehabilitation is a behavioral therapeutic approach for enhancing the neural control of task performance. Our neurorehabilitation intervention for walking will incorporate many evidence-based principles of motor recovery including:

*Restoration of function:* We seek to restore walking function through neuroplastic adaptations of locomotor circuitry. We will discourage the use of compensatory movement strategies or assistive devices because such approaches may limit or counteract the neurophysiological adaptations that we seek to promote.

*Specificity of training:* Rehabilitation is most effective when targeting specific neural circuits that underlie behavioral deficits.

*Sensory input to the nervous system:* Sensory input in this context refers to movement strategies that promote task-appropriate afferent activity. A number of proprioceptive and somatosensory factors are known to be important for triggering initiation and performance of gait cycle events. These include achieving sufficient limb loading and leg extension to promote robust forward propulsion, followed by sufficient maximal hip extension to trigger the initiation of

swing phase. Therapists will emphasize appropriate body weight shifting and limb loading, hip extension and symmetry during key events/phases of the gait cycle.

*Intensity, Repetition and Progression of training:* Neuroplasticity requires repeated and intense practice. Furthermore, progression of intensity ensures a high training stimulus even as capability improves.

We will use two neurorehabilitation interventions: steady state walking (control intervention) and complex walking tasks (experimental intervention). The objective of the complex walking task intervention is to engage frontal/executive circuits to induce beneficial activity-dependent neuroplasticity (e.g., synaptic connectivity). We have previously shown that complex walking tasks are a potent approach for engaging prefrontal cortex during walking. Furthermore, complex walking tasks are important and ecologically valid because they are crucial to successful mobility in the home and community environments.

**Transcranial Direct Current Stimulation (tDCS) and augmentation of mobility and cognition**

tDCS will be used to induce positive neuromodulation of frontal/executive circuits to make them more amenable to the “activity-dependent neuroplasticity” that is known to occur with behavioral neurorehabilitation. Specifically, tDCS may facilitate the efficacy of our walking neurorehabilitation intervention by strengthening the synaptic connections within the recruited circuits. Deeper frontal circuits may also experience neuromodulation through applied field effects. tDCS involves the application of a weak electrical current through two or more electrodes placed on the scalp. The principal mechanism of action is subthreshold modulation of neuronal membrane potentials, which alters cortical excitability and neuronal activity dependent on the current flow direction through the target neurons. We propose that integrating anodal tDCS into a neurorehabilitation intervention will increase its effectiveness. Indeed, the neurocognitive literature reveals evidence that modulatory effects accumulate when tDCS is applied during multiple, consecutive sessions, and that tDCS effects are most prominent when a consolidation period is allowed. Furthermore, applying tDCS during practice of the desired functional task has been found to trigger effects that outlast the stimulation period and facilitate longer term neuroplasticity.

**5. Specific Aims:**

**Specific Aim 1: Determine preliminary efficacy for recovery of mobility and cognitive function.**

Primary Mobility Outcome: Figure-of-eight walking test (Figure-8 Walk Test)

Primary Cognitive Outcome: Composite executive score on NIH EXAMINER battery (EXAMINER)

Hypothesis 1a: Effect sizes for improvement in the *Figure-8 Walk Test* will be greatest for *complex/active*, followed by *complex/sham*, followed by *standard/sham*.

Hypothesis 1b: Effect sizes for improvement on EXAMINER will be greatest for *complex/active*, followed by *complex/sham*, followed by *standard/sham*.

**Specific Aim 2: Demonstrate feasibility/safety of tDCS as an adjuvant to rehabilitation.**

Hypothesis 2: The study interventions will not significantly differ for adherence, retention, or adverse events.

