## **6. Research Plan:**

### Study Overview

All study procedures will be conducted at the University of Florida.

Up to thirty older men and women will be enrolled in the intervention component of this study. A larger number will be enrolled for onsite screening, because some will fail the screening tests and not proceed to the study intervention. Volunteers will undergo the following sequence of events:

- *Telephone Screening*: Volunteers will be screened by telephone to determine if they meet basic enrollment criteria including age and general health status.
- *1st Informed Consent and Onsite Screening*: Volunteers who pass the phone screen will be invited to participate in on-site screening. Informed consent for screening will be obtained. Mobility function and cognitive screening will be conducted, including 10m walk speed and tests from the cognitive battery of the NIH Toolbox. Other criteria listed in Table 6 will also be evaluated. Screening will be conducted over two visits lasting approximately 4 hours and 3 hours, respectively. A third visit may sometimes be needed if all assessments cannot be completed in the two visits
- *2nd Informed Consent and Baseline Assessment*: Qualifying volunteers will be invited to participate in the full study. They will attend a baseline assessment session which will include Informed Consent for full study participation and tests of the primary and secondary study outcomes including Figure-8 walk test and NIH EXAMINER battery of executive function. Secondary outcomes will also be evaluated as described in the Research Plan. This visit will last approximately 3 hours.
- *Rehabilitation Intervention*: Enrolled participants will receive 18 sessions of neurorehabilitation, which will be combined with either active or sham tDCS. These sessions will be completed over the course of 6 weeks. Each session will last about 75 minutes from arrival to departure.
- *Post-Intervention Assessment*: At the completion of the neurorehabilitation program, participants will attend a post-therapy assessment session that is identical to the baseline assessment.
- *Three month follow up Assessment*: Three months after completing the neurorehabilitation program, participants will attend a 3-month follow up assessment session that is identical to the baseline and post-treatment assessments.

---

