### **Rehabilitation Intervention**

Participants will take part in a 6-week, 18-session neurorehabilitation led by qualified and trained study personnel. Participants will be randomized to one of three groups: 1) standard walking neurorehabilitation with sham tDCS ('standard/sham' group), 2) complex walking neurorehabilitation with sham tDCS ('complex/sham' group), or 3) complex walking neurorehabilitation with active anodal tDCS ('complex/active' group). Training logs will be maintained to gauge the content and intensity of training. To control for intensity, participants will maintain a rating of perceived exertion of 4 (moderate to strong) on the Borg Category/Ratio Scale during walking. Exertion will be adjusted by modifying walking speed and/or by modifying the rest time between walking bouts. Training logs will also include information on attendance and adverse events. From these logs we will determine adherence (# of sessions attended), retention (completion of rehabilitation and post-therapy assessment) and number of adverse events.

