## **10. Statistical Analysis Plan**

This is an R21 study that is designed to acquire data for planning a full scale clinical trial. Summary statistics will be provided for all primary measures, as well as for demographic and clinical characteristics. For the primary outcome of each hypothesis, group mean differences and standard deviations will be used to calculate effect sizes. With this information we will be able to conduct a power analyses to plan for a future full-scale clinical trial.

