## **Data and Safety Monitoring Plan**

### ***Data Safety Monitoring Board***

This study will use the Pepper Safety Committee for data and safety monitoring. This committee, henceforth called the Data Safety Monitoring Board (DSMB) is used for most studies that are affiliated with the UF Claude Pepper Older Americans Independence Center. The three members of this committee have no affiliation with the study. The committee meets every 6 months.

The PI will provide the DSMB with access to all relevant study data, documents and progress information. The PI and designated staff will attend the DSMB meetings and will be responsible for preparing and presenting data reports from the study.

The DSMB has the following charges:

- The initial task of the DSMB is to review the study protocol with regard to recruitment, randomization, intervention, subject safety, data management, plans for auditing of subject records, quality control and analysis plans, and to identify needed modifications. The DSMB then identifies the relevant data parameters and the format of the information to be regularly reported.
- Review data over the course of the trial relating to recruitment, randomization, compliance, retention, protocol adherence, trial operating procedures, forms completion, intervention effects, gender and ethnic/racial minority inclusion and subject safety.

- Identify problems relating to safety over the course of the study. Inform study PI via written report.
- Identify needs for additional data relevant to safety issues and request these data from the study investigators.
- Propose appropriate analyses and periodically review developing data on safety and endpoints.
- Make recommendations regarding recruitment, treatment effects, retention, compliance, safety issues and continuation of the study.
- Send the Program Administrator and PI written reports following each DSMB meeting. These reports may address all issues reviewed by the DSMB.
- The study PI is responsible for distributing the report to the local IRB.

The DSMB may convene an executive session at any time. The PI, project director, and project officer would attend these meetings. Any additional requirements pertaining to the DSMB will be determined by the NIA.

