### ***Adverse Event Reporting***

Adverse events (including expected, unexpected, serious and non-serious) will be tracked in a cumulative table. Adverse events will be reported according to the guidelines of the University of Florida Institutional Review. Specifically, adverse events that are serious and unexpected (see definitions below) will be reported to the UF IRB within 5 working days of when study personnel learned about it. Reports of adverse events that are not serious or that are expected (e.g., muscle soreness) will be added to the cumulative adverse event table and reported to the UF IRB annually.

A *serious adverse event* is any adverse event that results in any of the following outcomes:

- death,
- a life-threatening adverse event,
- inpatient hospitalization or prolonging existing hospitalization,
- a persistent or significant disability/incapacity,
- or a congenital anomaly/birth defect.

Important medical events that may not result in death, be life-threatening, or require hospitalization may be considered a serious adverse event when the event may jeopardize the patient or subject and/or may require medical or surgical intervention to prevent one of the outcomes listed in the definition above.

An *unexpected adverse event* is any adverse event that is not consistent with the current investigator brochure, protocol, consent form, or is not part of the normal disease progression. In addition, known adverse events may occur more frequently than expected. If so, then this meets the definition of “unexpected” and must be reported to the IRB.

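### Aim 2 sets out to demonstrate tDCS feasibility and safety, but its only yardstick is a non-significant difference between arms of about 10, which cannot by itself show either

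*Combined protocol and SAP*

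**What the plan says.** The Abstract gives the purpose: "The objective of this study is to calculate effect size, establish variance of response and demonstrate feasibility of the experimental interventions". It adds: "The data collected here will provide the information needed to justify and plan a future full scale clinical trial".

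Under Specific Aim 2, which is to demonstrate feasibility and safety of tDCS, the only hypothesis is: "Hypothesis 2: The study interventions will not significantly differ for adherence, retention, or adverse events".

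The three measures are defined under Rehabilitation Intervention: "From these logs we will determine adherence (# of sessions attended), retention (completion of rehabilitation and post-therapy assessment) and number of adverse events". No acceptable level is set for any of them.

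Section 10 (Statistical Analysis Plan) promises summary statistics and then: "For the primary outcome of each hypothesis, group mean differences and standard deviations will be used to calculate effect sizes". It names no test, significance level, margin, interval or target for Hypothesis 2.

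On safety, Adverse Event Reporting says: "Adverse events (including expected, unexpected, serious and non-serious) will be tracked in a cumulative table". The monitoring board's charges include: "Propose appropriate analyses and periodically review developing data on safety and endpoints". Neither is a criterion for Aim 2.

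On size, the Study Overview says: "Up to thirty older men and women will be enrolled in the intervention component of this study". There are three arms, only one of which receives active tDCS during the intervention. The allocation ratio is not stated.

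**The concern.** The aim is to demonstrate something, and the only condition attached to it is the absence of a significant difference. Failing to reject a null hypothesis is not evidence that it is true, and with about 10 per arm non-significance is the usual result even when the active arm does materially worse on drop-out. The condition therefore says little about whether tDCS is tolerable enough to carry forward.

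The results are meant to justify a full-scale trial. If Aim 2 is followed as written, an uninformative comparison of drop-out, adherence or uncommon events would count in favour of going ahead, and the planners of the next trial would not see how uncertain it was.

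Two smaller gaps add to this. The hypothesis turns on significance, yet no test is specified. The effect size in section 10, built on mean differences and standard deviations, does not fit retention, which is a proportion.

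**Working it through.** The plan has no power, margin or precision figure for Aim 2, so there is nothing of its own to reproduce.

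**Inputs from the documents.** At most 30 participants (Study Overview), three arms and 18 sessions (Rehabilitation Intervention). 30 / 3 = 10 per arm.

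**Assumed, because the documents are silent.** Equal allocation, two-sided 5% level, and the drop-out rates, standard deviations and event rates below.

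**1. Retention.** For arms of size n_A and n_S with true drop-out p_A and p_S, sum over all possible counts:

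P(non-significant) = Σ Bin(a; n_A, p_A) × Bin(b; n_S, p_S), over pairs (a, b) whose p-value exceeds 0.05.

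With Fisher's exact test:

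| True drop-out, sham v active | Complex/active v complex/sham (10 v 10) | Active v pooled sham (10 v 20) |
|---|---|---|
| 10% v 10% | 99.9% | 98.7% |
| 5% v 15% | 99.4% | 91.5% |
| 10% v 30% | 94.3% | 77.4% |
| 10% v 40% | 84.8% | 57.9% |
| 20% v 60% | 74.7% | 46.3% |

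*Choice of test.* Over Fisher, Boschloo, Barnard and uncorrected Pearson tests and both contrasts, 10% v 30% is non-significant 73% to 94% of the time, against 96% to 99.9% when drop-out is equal at 10%. Comparing all three arms at once gives 88% (Fisher-Freeman-Halton) or 78% (Pearson) for 10% v 30%, against 99% and 96% when equal.

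*Unequal arms.* With each complex arm of any size from 8 to 12, the pairwise Fisher figure for 10% v 30% runs from 84% (11 active, 12 sham) to 97% (8 and 8).

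**2. One concrete result.** Suppose 1/10 drop out on complex/sham and 5/10 on complex/active, six in all among 20.

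- P(5 in active) = C(10,5) × C(10,1) / C(20,6) = 2520 / 38760 = 0.0650
- P(6 in active) = C(10,6) / C(20,6) = 210 / 38760 = 0.0054
- Two-sided p = 2 × (0.0650 + 0.0054) = 0.14

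Boschloo and Barnard tests give 0.062 and Pearson 0.051. Hypothesis 2 is met for this pair with half the active arm lost. Pooling the sham arms (2/20 v 5/10) gives Fisher p = 0.026, so the verdict also depends on a contrast that the plan does not name.

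**3. No events seen.** With 0/10 events the exact two-sided 95% upper limit is 1 − 0.025^(1/10) = 0.308, so a true rate up to 31% is compatible.

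**4. Adherence.** For a two-sample t-test with 10 per arm the noncentrality is d × √(10/2), on 18 degrees of freedom. Power reaches 80% at d = 1.325. With an assumed SD of 2 to 4 sessions, that is 1.325 × 2 = 2.65 to 1.325 × 4 = 5.3 of the 18 sessions.

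**5. Adverse-event counts.** With Poisson counts per person and an exact conditional test, 0.1 v 0.3 is missed 96% of the time, 0.3 v 0.9 69%, and 1 v 3 13%. Uncommon events are the problem; a large rise in frequent events would usually be detected.

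**The case against.** The strongest reply is that Hypothesis 2 is an expectation rather than a decision rule. Hypotheses 1a and 1b likewise only predict an ordering, section 10 names no significance test at all, and the trial is declared a planning study. Description is already planned, through adherence and retention counts, summary statistics and a cumulative adverse-event table. The monitoring board reviews analysis plans and safety, so safety does not rest on a p-value alone. All of that is fair, and it limits the point. It does not remove it, because Aim 2 offers no other criterion.

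Four stronger readings are tempting and are not supported:

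- *The sponsor will report non-significance as success.* No section says so.
- *The trial is too small.* Its stated purpose is planning, and 30 participants are acceptable for that.
- *The hypothesis is met almost as often when drop-out triples as when it is equal.* That holds only for the pairwise Fisher test (94% v 99.9%), the most conservative choice. Pooling the sham arms separates the cases more clearly (77% v 99%).
- *Any excess of harm would be missed.* Large increases in frequent events, possibly including the itching and tingling listed under tDCS Safety, would usually show.

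**Conclusion.** The point holds as a fault in the inference rule and should be fixed. For drop-out, adherence and uncommon adverse events, non-significance at about 10 per arm cannot by itself support feasibility or safety, and the plan supplies nothing else to judge them by.

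The percentages are illustrations. They rest on assumed rates, a two-sided 5% level and near-equal arms, and the retention figures concern that outcome alone. They are therefore upper bounds on the chance that all three outcomes are non-significant together. What does not depend on the exact assumptions is the direction: for a tripling of drop-out from 10% to 30%, non-significance is the usual result under every test, contrast and arm size tried. Thirty is a ceiling, so enrolment may also fall short of 10 per arm.

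**What to change.** Replace Hypothesis 2 with an estimation objective, and carry it into section 10:

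- For each arm, report with 95% confidence intervals: sessions attended, retention (exact interval), the number of adverse events as already defined, and the proportion of participants with at least one event (exact interval). Show serious events separately. Keep the count beside the proportion, because if mild sensations are logged as events the proportion could approach its ceiling in every arm.
- Report the complex/active minus complex/sham difference with its 95% interval. This contrast isolates tDCS.
- Judge feasibility against numerical targets that the sponsor sets before outcome data are examined by arm. State in advance whether the point estimate or a confidence limit must meet the target.
- State that non-significance will not be interpreted as no difference.

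The cost is wording in Aim 2 and section 10, with no new participants or data. The downside is a less favourable feasibility and safety statement, because the intervals are wide. For 9/10 retained, the exact 95% interval is 55% to 99.7%; for 27/30 across arms it is 73% to 98%. Equal drop-out of 0, 1 or 2 of 10 in both arms still leaves the difference uncertain by about ±28, ±31.5 or ±34 percentage points (Newcombe). The choice between point estimate and confidence limit can therefore decide the outcome, which is why it must be fixed beforehand.
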